This pilot study will be conducted in accordance with International Conference on Harmonisation Good Clinical Practice (ICH GCP), applicable US Code of Federal Regulations (CFR). As the Sponsor-Investigator, the PI will assure that no deviation from, or changes to the protocol, will take place without prior agreement from the investigational drug sponsor Global Blood Therapeutics, and documented approval from the IRB, except where necessary to eliminate an immediate hazard(s) to the study participants. All personnel involved in the conduct of this study have completed Human Subjects Protection and ICH GCP Training.

The protocol, informed consent form(s), recruitment materials, and all participant materials will be submitted to the IRB for review and approval. Approval of both the protocol and the consent form will be obtained before any participant is enrolled. Any amendment to the protocol will be reviewed and approved by the IRB before the changes are implemented to the study. All changes to the consent form will be IRB approved.

1 PROTOCOL SUMMARY

1.1 SYNOPSIS

Title:

The Effect of Voxelotor on Exercise Capacity of Youths with Sickle Cell Anemia

Study Description:

This study is a pilot, open-label, single-arm study to evaluate the effect of voxelotor on exercise capacity, as measured by cardiopulmonary exercise testing (CPET) in patients 12 years of age and older with sickle cell anemia (SCA). Voxelotor was recently approved for the treatment of SCA in patients 12 years and older. We hypothesize that exercise capacity will be improved by voxelotor treatment in sickle cell patients whether they are on Hydroxyurea or not. This study will assess exercise capacity by cardiopulmonary exercise testing (CPET) before and after 8 weeks of voxelotor therapy.

Objectives:

Primary Objective: To evaluate the effect of voxelotor on peak oxygen consumption (VO₂) in adolescents with SCA as assessed by change in CPET from baseline.

Secondary Objective: To correlate peak VO₂ with biochemical markers, including hemoglobin, reticulocyte count, bilirubin, lactate dehydrogenase, haptoglobin, % Hgb F expressing cells, P50 oxygen dissociation, point of sickling (POS), and dense cells.

Exploratory Objective: To evaluate the effect of voxelotor on HRQOL as assessed by patient-reported outcome (PGIC) and clinician-reported outcome (CGIC) at end of treatment study visit

Endpoints:

Primary endpoint: Change in Peak VO₂ from baseline

Secondary endpoint: Hemoglobin and biochemical markers of sickling and hemolysis

[figure not shown]
Exploratory endpoint: Clinician and Patient Global Impression of Change assessment (CGIC and PGIC)

Study Population:

1.1.1.1.1 Patients seen in the Pediatric Sickle Cell Program in Northern Virginia (Fairfax, VA) who have a genetically severe forms of sickle cell disease (including Hgb SS, Hgb Sbeta⁰thalassemia, or Hgb SC^{Harlem}) and are age 12 or older.

| | |
|--|--|
| Phase: | This is a single-center, open-label, single-arm longitudinal interventional pilot study. |
| Description of Sites/Facilities Enrolling Participants: | The outpatient sickle cell clinic of Pediatric Specialists of Virginia located in the Schar Cancer Institute on Inova Hospital Campus in Fairfax, VA. This pilot study aims to enroll 10 patients. |
| Description of Study Intervention: | During the open-label treatment period, all participants will receive voxelotor at a fixed dose of 1500mg (administered as three 500mg tablets) orally once daily for 8 weeks |
| Study Duration: | 12 months |
| Participant Duration: | 6 months |

1.2 SCHEMA

1.3 SCHEDULE OF ACTIVITIES (SOA)

| Procedures | Screening/ Enrollment Day -60 | Study Visit 1 Day -30 +/- 7 days | Study Visit 2 Day - 29 to -1 | Study Visit 3 Day 1 +/- 14 days | Study Visit 4 Day 30 +/- 7 days | Study Visit 5 Day 60 +/- 7 days | Study Visit 6 Day 60-89 | Final Study Visit 7 Day 90 +/- 14 days |
|--|-------------------------------------|--|------------------------------------|---------------------------------------|---------------------------------------|---------------------------------------|----------------------------|---|
| Informed consent | x | | | | | | | |
| Demographics | x | | | | | | | |
| Medical history | x | | | | | | | |
| Dispense voxelotor ^d | | | | x | x | x ^d | | |
| Concomitant Medication review | x | x | | x | x | x | | x |
| Physical exam | x | x | | x | x | x | | x |
| Vital signs, Ht, Wt | x | x | x | x | x | x | x | x |
| Performance status | x | | | | | x | | x |
| Routine labs ^a | x | x | | x | x | x | | x |
| Study labs ^b | | x | | | | x | | |
| Pregnancy test ^c | x | | | x | x | x | | |
| Adverse event review and evaluation | x | | | x | x | x | | x |
| Schedule CPET | | x | | | | x | | |
| CPET | | | x | | | | x | |
| CGI, PGI assessments | | | | | | | | x |
| Data collection and entry | x | x | | x | x | x | | x |

^a Routine labs: CBC diff, retic, CMP, LDH, haptoglobin, Hemoglobin F or hemoglobin electrophoresis

^b Study labs: Send to UCSF [name] lab: % F cells, P50 oxygen dissociation, ektacytometry, point of sickling (POS), dense cells.

^c Pregnancy test: All menstruating female participants

^d Participants will be treated with voxelotor for at least 8 weeks before the 2nd CPET, which will be scheduled as close to the date following 8 weeks of treatment with voxelotor. Participants will continue voxelotor until the 2nd CPET is completed.

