5 STUDY POPULATION

5.1 INCLUSION CRITERIA

Subjects will be recruited from the Pediatric Specialists of Virginia Sickle Cell Program.

In order to be eligible to participate in this study, an individual must meet all of the following criteria:

1. Provision of signed and dated informed consent form
2. Stated willingness to comply with all study procedures and availability for the duration of the study
3. Male or female, age \geq 12 years
4. In good general health as evidenced by medical history and diagnosed with a genetically severe form of sickle cell anemia (Hgb SS, Hgb S beta 0 thalassemia, Hgb SC^{Harlem}, and others)

5. Patients who are on Hydroxyurea need to be on a stable dose for at least 3 months without anticipated change in dosing until the study is completed.
6. Ability to take oral medication and willingness to adhere to daily voxelotor and 2 CPETs at scheduled intervals.
7. For females of reproductive potential who are sexually active: use of highly effective contraception for at least 1 month prior to screening and agreement to use such a method during study participation and for an additional 30 days after the end of study.
8. For males of reproductive potential: use of condoms or other methods to ensure effective contraception with partner

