6.4 STUDY INTERVENTION COMPLIANCE

Each bottle of voxelotor contains 90 tablets. The dose is 3 tablets a day. Each bottle lasts 30 days. Participants will be scheduled for clinic visits no longer than 30 days apart. Participants will be given a bottle of voxelotor at a clinic visit and will be asked to bring back the bottle with left over pills in it. Compliance will be determined by pill counting. The number of pills remaining will be counted and subtracted from 90 to get the number of pills taken, which can be divided by 3 to get the number of days the drug was taken. The difference between the number of days drug was taken and the number of days between the clinic visits is the number of days drug was missed.

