8.3.2 DEFINITION OF SERIOUS ADVERSE EVENTS (SAE)

An AE or suspected AE is considered “serious” if it results in any of the following outcomes: death, a life-threatening adverse event, inpatient hospitalization, a persistent or significant incapacity or substantial disruption of the ability to conduct normal life functions, or any event that may jeopardize the

participant or require medical or surgical intervention. An AE for this study may be a hypersensitivity reaction in the form of bronchospasm requiring intensive treatment in the emergency room or clinic or result in hospitalization.

8.3.3 CLASSIFICATION OF AN ADVERSE EVENT.

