8.3.4 TIME PERIOD AND FREQUENCY FOR EVENT ASSESSMENT AND FOLLOW-UP

Example text provided as a guide, customize as needed:

The occurrence of an adverse event (AE) or serious adverse event (SAE) may come to the attention of study personnel during study visits and interviews of a study participant presenting for medical care, or upon review by the study PI.

All AEs including local and systemic reactions not meeting the criteria for SAEs will be captured on the appropriate study database form. Information to be collected includes event description, time of onset, clinician’s assessment of severity, relationship to study product (assessed only by those with the training and authority to make a diagnosis), and time of resolution/stabilization of the event. All AEs occurring while on study must be documented appropriately regardless of relationship. All AEs will be followed to adequate resolution.

Any medical condition that is present at the time that the participant is screened will be considered as baseline and not reported as an AE. However, if the study participant’s condition deteriorates at any time during the study, it will be recorded as an AE.

Changes in the severity of an AE will be documented to allow an assessment of the duration of the event at each level of severity to be performed. AEs characterized as intermittent require documentation of onset and duration of each episode.

The study coordinator will record all reportable events with start dates occurring any time after informed consent is obtained until 7 (for non-serious AEs) or 30 days (for SAEs) after the last day of study participation. At each study visit, the investigator will inquire about the occurrence of AE/SAEs since the last visit. Events will be followed for outcome information until resolution or stabilization.

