8.3.9 REPORTING OF PREGNANCY

In the event of pregnancy that occurs during study, the pregnancy will be reported to GBT Pharmacovigilance or Designee and the decision for the participant to continue on study or not will depend on the specific situation and will be discussed with GBT Pharmacovigilance or Designee.

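### The last on-drug interval, Visit 5 to the second exercise test, is the only one with no later scheduled pregnancy test; a test at Visit 7 would be a cheap addition (minor, safety only)

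*Protocol*

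**What the plan says.** **Testing and dosing.** In the Schedule of Activities (Protocol 1.3) the pregnancy-test row reads "Pregnancy test ^c | x | | | x | x | x": Screening, then Visits 3, 4 and 5, with Visits 6 and 7 blank. Footnote c applies it to all menstruating female participants. Footnote a lists the routine labs and includes no pregnancy test. Voxelotor is dispensed at Visits 3, 4 and 5. Footnote d requires at least 8 weeks of treatment before the second CPET, "which will be scheduled as close to the date following 8 weeks of treatment with voxelotor", and adds: "Participants will continue voxelotor until the 2nd CPET is completed". That CPET is Visit 6. Section 6.4 limits the gaps between visits: "Participants will be scheduled for clinic visits no longer than 30 days apart".

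**Contraception and reporting.** Inclusion criterion 7 (section 5.1) asks sexually active females of reproductive potential for "agreement to use such a method during study participation and for an additional 30 days after the end of study". Section 8.3.9 sets the reporting duty: "In the event of pregnancy that occurs during study, the pregnancy will be reported". Section 8.3.4 records events "until 7 (for non-serious AEs) or 30 days (for SAEs) after the last day of study participation" and does not name pregnancy. The serious outcomes in section 8.3.2 begin with "death, a life-threatening adverse event, inpatient hospitalization, a persistent or significant incapacity". They end with a broader limb for events that could endanger the participant or call for medical or surgical treatment.

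**The concern.** The protocol treats pregnancy as an exclusion (5.2), a reason for withdrawal (7.2) and an event to report to pharmacovigilance (8.3.9). These provisions work only if a pregnancy is found. One that begins after the Visit 5 test, while the participant is still on drug, would come to light through symptoms, self-report, or the examination and adverse event review at Visit 7. Participants may be as young as 12, so self-report is a weak safeguard.

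A second, lesser point is that the contraception requirement outlasts the pregnancy reporting duty by 30 days. The protocol asks for contraception in that period but does not say what to do if it fails.

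The stake is safety ascertainment. Peak VO₂, its analysis and the sample size are untouched.

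**Working it through.** The protocol states no figure of its own for this gap, so the check uses the visit windows.

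**Inputs** (Schedule of Activities, footnote d, section 6.4)

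- Visit 3, first dose: Day 1 ± 14, so at the latest Day 15.
- Visit 5, last scheduled test: Day 60 ± 7, so Day 53 to 67.
- Visit 6, second CPET and last dose: Day 60 to 89.
- Visit 7: Day 90 ± 14, so Day 76 to 104.
- At least 8 weeks (56 days) from first dose to second CPET.
- Clinic visits at most 30 days apart, and Visit 5 ≤ Visit 6 ≤ Visit 7.

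**Step 1. Which dosing intervals end at a test?**

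| On-drug interval | Next scheduled test |
|---|---|
| Visit 3 to Visit 4 | Visit 4 |
| Visit 4 to Visit 5 | Visit 5 |
| Visit 5 to second CPET (Visit 6) | none |

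**Step 2. Last test to last dose, with the CPET as early as allowed.** Earliest Visit 6 = max(Day 60, Visit 5, Visit 3 + 56).

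- First dose Day 1: 1 + 56 = Day 57, so the Day 60 limit governs. Visit 5 on Day 53 gives 60 − 53 = 7 days. Visit 5 on Day 60 gives 0, and a later Visit 5 also gives 0 because the CPET can be the same day. Range: **0 to 7 days**.
- Visit 3 on Day 15, other windows fixed on the original calendar: 15 + 56 = Day 71. Visit 5 on Day 67, 60 or 53 gives 71 − 67 = 4, 71 − 60 = 11 or 71 − 53 = 18 days. Upper end: **18 days**.

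The protocol does not say whether later windows move with the actual first dose, so both ranges are shown.

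**Step 3. Outer limit.** The raw windows would allow 89 − 53 = 36 days. But Visit 7 may be at most 30 days after Visit 5, and the CPET cannot follow Visit 7, so the gap is at most **30 days** (for example Visit 5 on Day 59 and CPET on Day 89).

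**Step 4. Where a Visit 7 test would fall.**

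- After the Visit 5 test: 76 − 67 = 9 days at least, and 30 at most by the spacing rule.
- After the last dose, over all permitted dates: 0 to 30 days.
- First dose Day 1 and earliest CPET: the spacing rule puts Visit 5 no later than 1 + 30 + 30 = Day 61, so the CPET is on Day 60 or 61. Visit 7 then falls 76 − 61 = 15 to 90 − 60 = 30 days after the last dose.
- The 18-day case (Visit 5 Day 53, CPET Day 71): Visit 7 lies between Day 76 and 53 + 30 = Day 83, which is 5 to 12 days after the last dose.

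If a test within about two weeks of conception may be negative (an assumption; the protocol gives no detection lag), a Visit 7 test works well on the usual schedule and less well when the CPET is late.

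**Step 5. The post-study period.** Under section 4.4 completion includes Visit 7, nominally Day 90. The extra 30 days of contraception run to Day 120. With the CPET near Day 60, that is 90 − 60 = 30 to 120 − 60 = 60 days after the last dose. Over all permitted dates it is 0 to 60 days.

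**The case against.** The best defence is that the schedule follows a coherent rule: test at Screening and whenever drug is handed out. Tests and dispensing do coincide at Visits 3, 4 and 5, so nothing is misstated, and a further test is extra surveillance. It is true that the rule is coherent and that every dispensing is preceded by a test at the same visit. But testing before dispensing does not check the interval that follows, and only the last interval lacks that check.

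Other safeguards exist. Section 8.2 gives every visit an examination and adverse event assessment, although the Schedule of Activities marks these at Visit 7 and not at Visit 6. Section 8.3.4 requires inquiry about events at each visit, and section 5.5 promises constant telephone contact. These reduce the concern, but none is a test.

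On reporting, eligibility and reporting are different duties and need not share a period. Section 2.3.1 expects no long-term risk once the drug is stopped, and the post-study days nominally begin 30 days after the last dose. This stands, and makes the second point secondary.

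Stronger readings are tempting, and the documents do not support them:

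- *That up to 36 days on drug go unchecked.* This ignores the 30-day spacing in section 6.4.
- *That an on-drug conception discovered after the study escapes reporting.* It occurred during the study, so section 8.3.9 already covers it.
- *That sections 8.3.2, 8.3.4 and 8.3.9 contradict one another, or that a post-study pregnancy can never be reported.* They do not conflict. A complicated pregnancy could qualify as serious, including through the broad last limb of 8.3.2, and be recorded within 30 days. What has no stated duty is an uncomplicated pregnancy that begins after the study.

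**Conclusion.** The gap in testing is real but small. One on-drug interval has no later scheduled pregnancy test. It lasts 0 to 7 days at the earliest CPET if Day 1 is the first dose, up to 18 days if Visit 3 slips to Day 15 on a fixed calendar, and at most 30 days. The mismatch between contraception and reporting is a secondary matter of alignment, not a contradiction.

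The conclusion assumes that the section 6.4 spacing rule is kept and that Visit 6 is the last dosing day. The number of menstruating participants is not given; anything from 0 to 10 of the 10 planned is possible. This is a minor, inexpensive improvement to safety monitoring, with no bearing on any estimate or test.

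**What to change.** **(a) Main change.** In the Schedule of Activities, pregnancy-test row, add a cross under Final Study Visit 7. Routine labs are already drawn there, so no visit is added. The cost is at most 10 extra tests, one per eligible participant among the 10 planned. It would find most, not all, pregnancies begun in the last dosing interval: a test within about two weeks of the last dose may miss a very recent conception. It does not prevent exposure.

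**(b) Secondary change.** In section 8.3.9, after the words limiting the duty to pregnancies during study, insert *or within 30 days after the end of study*. Reporting then covers the same period as contraception in inclusion criterion 7. The cost is one clause. Because no contact is scheduled after Visit 7, it depends on the participant telling the site, and she should be asked at Visit 7 to do so.

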2 INTRODUCTION

2.1 STUDY RATIONALE

The beta globin mutation in sickle cell disease leads to production of sickle hemoglobin (HbS) that in the deoxygenated state polymerizes and results in sickling and hemolysis of red blood cells. Studies have shown that children and adults with sickle cell anemia (SCA) exhibit decreased cardiopulmonary fitness. While multiple factors influence exercise capacity, anemia is directly related to oxygen-carrying capacity and is one factor that affects cardiopulmonary fitness. Low exercise capacity in SCA is partly due to low hemoglobin. Voxelotor is a recently approved therapy for SCA, shown to decrease hemolysis and increase hemoglobin in untreated as well as Hydroxyurea-treated SCA patients. Increasing hemoglobin is expected to increase oxygen carrying capacity, therefore, treatment with voxelotor is expected to improve exercise capacity.

2.2 BACKGROUND

Why do we need to know about exercise tolerance in SCA?

Physical activity has been significantly limiting for patients with sickle cell anemia. Whereas people with sickle cell trait (SCT) engage in high intensity athletics and military training, individuals with sickle cell anemia (SCA) have not participated, either due to patients' own inability to tolerate exercise or restrictions placed upon them by others, or a combination of factors^{1,2}. In the era of hydroxyurea, lifestyles for many SCA patients have improved. In our own pediatric sickle cell program, which has a high hydroxyurea usage rate, many children are described by their parents as being as active as other children, and some teenagers participate in team sports and even try out for varsity sports, including football. As sickle cell providers, we are often asked by school athletic departments to sign sports clearance forms and list specific restrictions for the student with sickle cell disease. While organizations such as NCAA provide general guidelines for SCT, no published specific guidelines exist for SCA^{3,4}. What is known about SCT, i.e., increased risk of exertional rhabdomyolysis, is not directly applicable to SCA, which presents distinct challenges, not the least of which appears to be limited physical ability. Yet, regular exercise has been shown to improve health in chronic illnesses, including sickle cell disease^{1, 5-9}. Increasingly, demonstration that exercise is beneficial in SCA is prompting SCA healthcare providers to encourage their patients to be physically active. Given SCA youths' desire to be athletic and the advocacy for physical exercise in SCA, understanding the exercise capacity in SCA is increasingly necessary.

How is exercise capacity measured?

Cardiopulmonary exercise testing, or CPET, is the commonly accepted benchmark of aerobic capacity^{10, 11}. While a subject is performing a standardized exercise protocol with incremental ramping, either on a bicycle or a treadmill, and breathing through a non-rebreathing mouthpiece, expired air is analyzed via breath-by-breath sampling. Fractions of oxygen, carbon dioxide, air volume and flow are measured to calculate oxygen uptake (VO₂), carbon dioxide output (VCO₂) and minute ventilation, all in real-time. The peak VO₂ (VO₂ max) is the maximal ability of the subject to take in and utilize oxygen, which is the functional aerobic exercise capacity. Peak VO₂ is determined by the cardiovascular, pulmonary, musculoskeletal, as well as the hematologic system. CPET is most commonly done in adults, but is also utilized in children, particularly in those with cystic fibrosis and congenital heart disease, as well as in adolescents with sickle cell disease¹².

What is known about exercise testing in SCA?

Although reports are limited, exercise in SCA has been investigated, and the field is growing. Experience in these investigations, including GBT's phase 1/2 voxelotor study, has reassured that maximal exercise testing is safe in SCA and does not induce pain or other sickle cell crisis^{1, 8, 13, 14, 24}. Studies have shown that children and adults with SCA exhibit decreased cardiopulmonary fitness, most informatively demonstrated through cardiopulmonary exercise testing (CPET) and peak oxygen consumption. Peak VO₂ in adolescents and adults with SCA in ergometric bicycle CPET was as much as 30% lower than controls, even after adjusting for BMI and hemoglobin^{15, 16, 17}. A study of more than 200 adults with SCA using a standard Balke treadmill exercise test found lower exercise capacity among participants than the general African American population, with lower exercise capacity associating with lower hemoglobin^{14, 18}. SCA is a systemic disease affecting all organs, and decreased peak VO₂ is likely multi-factorial. Anemia directly affects oxygen-carrying capacity, and low hemoglobin would be expected to compromise aerobic activity. Indeed, CPET before and after transfusion both in patients with chronic anemia conditions and in pre-surgical patients with anemia showed ~10% difference in

peak VO₂^{19,20}. Thus, low hemoglobin in SCA is likely one factor contributing to decreased exercise capacity, and increasing hemoglobin in SCA might improve VO₂ max.

Can medical therapy improve exercise capacity of sickle cell patients?

Our clinical experience suggests that physical ability is improved in young patients treated with Hydroxyurea, but this has not been documented. Voxelotor can further raise hemoglobin in untreated patients as well as patients already on Hydroxyurea²¹. Our patient population includes a cohort of teenagers eligible for treatment with voxelotor, and although most are on Hydroxyurea, not all respond with significant increases in hemoglobin. While an exercise study in 1997 found Hydroxyurea treatment correlated with better exercise performance²², more recently published exercise studies in SCA have not compared patients treated with and without Hydroxyurea. Regardless, one would expect that peak VO₂ would improve with voxelotor due to its positive effect on hemoglobin, as well as indirect effects of decreased sickling and hemolysis. In GBT's phase 1/2 voxelotor study, CPET was done in 12 adult sickle cell patients to address the concern that the higher O₂ affinity of drug-modified hemoglobin could negatively impact oxygen consumption. No significant change, either positive or negative, was observed in VO₂ max and ventilatory threshold, but the voxelotor doses used in that study were below GBT's currently recommended dose²⁴. Thus, the question of whether voxelotor treatment, at the currently recommended dose, could improve exercise capacity is unanswered.

This study aims to determine whether changes in peak VO₂ can be detected in youths with SCA after treatment with voxelotor.

